**13.4 Appendix IV ON-STUDY AUA SYMPTOM SCORE**

PLEASE FILL OUT THIS SHORT QUESTIONNAIRE TO HELP US FIND OUT MORE ABOUT ANY URINARY PROBLEMS YOU MIGHT HAVE. CIRCLE A NUMBER IN EACH COLUMN THAT BEST DESCRIBES YOUR SITUATION. YOU MUST ANSWER ALL QUESTIONS.

	Not at all	Less than one time in five	Less than half the time	About half the time	More than half the time	Almost always
1. Over the past month or so, how often have you had a sensation of not emptying your bladder completely after you finished urinating?	0	1	2	3	4	5
2. Over the past month or so, how often have you had to urinate again, less than two hours after you finished urinating?	0	1	2	3	4	5
3. Over the past month or so, how often have you found you stopped and started again several times when you urinated?	0	1	2	3	4	5
4. How often do you find it difficult to postpone urination?	0	1	2	3	4	5
5. Over the past month or so, how often have you had a weak urinary stream?	0	1	2	3	4	5
6. Over the past month or so, how often have you had to push or strain to begin urination?	0	1	2	3	4	5
	Not at all	Once every 8 hours	Once every 4 hours	Once every 3 hours	Once every 2 hours	At least once every hour
7. Over the past month or so, how often did you most typically get up at night to urinate?	0	1	2	3	4	5

**Total per column**      \_\_\_\_\_

\_\_\_\_\_  
Patient Name

\_\_\_\_\_  
Patient Signature

\_\_\_\_\_  
Date This Form was Completed

**13.5 Appendix V**

**EPIC**  
**The Expanded Prostate Cancer Index Composite**

This questionnaire is designed to measure Quality of Life issues in patients with Prostate cancer. To help us get the most accurate measurement, it is important that you answer all questions honestly and completely.

Remember, as with all medical records, information contained within this survey will remain strictly confidential.

Today's Date (please enter date when survey completed):

Month                  Day                  Year

**Name (optional):** \_\_\_\_\_

Date of Birth (optional): Month \_\_\_\_\_ Day \_\_\_\_\_ Year \_\_\_\_\_

**URINARY FUNCTION**

This section is about your urinary habits. Please consider **ONLY THE LAST 4 WEEKS**.

1. Over the **past 4 weeks**, how often have you leaked urine?

- More than once a day..... 1
- About once a day..... 2
- More than once a week..... 3 (Circle one number)
- About once a week..... 4
- Rarely or never..... 5

2. Over the **past 4 weeks**, how often have you urinated blood?

- More than once a day..... 1

- About once a day..... 2
- More than once a week..... 3 (Circle one number)
- About once a week..... 4
- Rarely or never..... 5

3. Over the **past 4 weeks**, how often have you had pain or burning with urination?

- More than once a day..... 1
- About once a day..... 2
- More than once a week..... 3 (Circle one number)
- About once a week..... 4
- Rarely or never..... 5

4. Which of the following best describes your urinary control **during the last 4 weeks**?

- No urinary control whatsoever..... 1
- Frequent dribbling..... 2 (Circle one number)
- Occasional dribbling..... 3
- Total control..... 4

5. How many pads or adult diapers per day did you usually use to control leakage **during the last 4 weeks**?

- None..... 0
- 1 pad per day..... 1
- 2 pads per day..... 2 (Circle one number)
- 3 or more pads per day..... 3

6. How big a problem, if any, has each of the following been for you **during the last 4 weeks**?  
(Circle one number on each line)

	No Problem	Very Small Problem	Small Problem	Moderate Problem	Big Problem
a. Dripping or leaking urine .....	0	1	2	3	4
b. Pain or burning on urination.....	0	1	2	3	4
c. Bleeding with urination.....	0	1	2	3	4
d. Weak urine stream or incomplete emptying.....	0	1	2	3	4

e. Waking up to urinate.....	0	1	2	3	4
f. Need to urinate frequently during the day .....	0	1	2	3	4

7. Overall, how big a problem has your urinary function been for you **during the last 4 weeks?**

- No problem..... 1
- Very small problem..... 2
- Small problem..... 3 (Circle one number)
- Moderate problem..... 4
- Big problem..... 5

### **BOWEL HABITS**

The next section is about your bowel habits and abdominal pain.  
Please consider **ONLY THE LAST 4 WEEKS.**

8. How often have you had rectal urgency (felt like I had to pass stool, but did not) **during the last 4 weeks?**

- More than once a day..... 1
- About once a day..... 2
- More than once a week..... 3 (Circle one number)
- About once a week..... 4
- Rarely or never..... 5

9. How often have you had uncontrolled leakage of stool or feces?

- More than once a day..... 1
- About once a day..... 2
- More than once a week..... 3 (Circle one number)
- About once a week..... 4
- Rarely or never..... 5

10. How often have you had stools (bowel movements) that were loose or liquid (no form, watery, mushy) **during the last 4 weeks?**

- Never..... 1
- Rarely..... 2
- About half the time..... 3 (Circle one number)
- Usually..... 4
- Always..... 5

11. How often have you had bloody stools **during the last 4 weeks?**

- Never..... 1
- Rarely..... 2
- About half the time..... 3 (Circle one number)
- Usually..... 4
- Always..... 5

12. How often have your bowel movements been painful **during the last 4 weeks?**

- Never..... 1
- Rarely..... 2
- About half the time..... 3 (Circle one number)
- Usually..... 4
- Always..... 5

13. How many bowel movements have you had on a typical day **during the last 4 weeks?**

- Two or less..... 1
- Three to four..... 2 (Circle one number)
- Five or more..... 3

14. How often have you had crampy pain in your abdomen, pelvis or rectum **during the last 4 weeks?**

- More than once a day..... 1
- About once a day..... 2
- More than once a week..... 3 (Circle one number)
- About once a week..... 4
- Rarely or never..... 5

15. How big a problem, if any, has each of the following been for you? (Circle one number on each line)

	No Problem	Very Small Problem	Small Problem	Moderate Problem	Big Problem
a. Urgency to have a bowel movement .....	0	1	2	3	4
b. Increased frequency of bowel movements....	0	1	2	3	4
c. Watery bowel movements.....	0	1	2	3	4
d. Losing control of your stools.....	0	1	2	3	4
e. Bloody stools .....	0	1	2	3	4
f. Abdominal/ Pelvic/Rectal pain.....	0	1	2	3	4

16. Overall, how big a problem have your bowel habits been for you **during the last 4 weeks?**

- No problem..... 1
- Very small problem..... 2
- Small problem..... 3 (Circle one number)
- Moderate problem..... 4
- Big problem..... 5

**SEXUAL FUNCTION**

The next section is about your **current** sexual function and sexual satisfaction. Many of the

questions are very personal, but they will help us understand the important issues that you face every day. Remember, **THIS SURVEY INFORMATION IS COMPLETELY CONFIDENTIAL.**

Please answer honestly about **THE LAST 4 WEEKS ONLY.**

17. How would you rate each of the following during the last 4 weeks? (Circle one number on each line)

	None	Poor	Fair	Good	Very Good
a. Your level of sexual desire?.....	1	2	3	4	5
b. Your ability to have an erection?.....	1	2	3	4	5
c. Your ability to reach orgasm (climax)?.....	1	2	3	4	5

18. How would you describe the usual QUALITY of your erections **during the last 4 weeks?**

- None at all..... 1
- Not firm enough for any sexual activity..... 2
- Firm enough for masturbation and foreplay only..... 3 (Circle one number)
- Firm enough for intercourse..... 4

19. How would you describe the FREQUENCY of your erections **during the last 4 weeks?**

- I NEVER had an erection when I wanted one..... 1
- I had an erection LESS THAN HALF the time I wanted one....2
- I had an erection ABOUT HALF the time I wanted one ..... 3 (Circle one number)
- I had an erection MORE THAN HALF the time I wanted one....4
- I had an erection WHENEVER I wanted one..... 5

20. How often have you awakened in the morning or night with an erection **during the last 4 weeks?**

- Never ..... 1
- Less than once a week..... 2
- About once a week..... 3 (Circle one number)
- Several times a week..... 4
- Daily ..... 5

21. **During the last 4 weeks**, how often did you have any sexual activity?

- Not at all..... 1
- Less than once a week..... 2
- About once a week..... 3 (Circle one number)
- Several times a week..... 4
- Daily ..... 5

22. **During the last 4 weeks**, how often did you have sexual intercourse?

- Not at all..... 1
- Less than once a week..... 2

- About once a week..... 3 (Circle one number)
- Several times a week..... 4
- Daily..... 5

23. Overall, how would you rate your ability to function sexually **during the last 4 weeks?**

- Very poor..... 1
- Poor..... 2
- Fair..... 3 (Circle one number)
- Good..... 4
- Very good..... 5

24. How big a problem **during the last 4 weeks**, if any, has each of the following been for you?  
(Circle one number on each line)

	No	Very Small	Small	Moderate	Big
	Problem	Problem	Problem	Problem	Problem
a. Your level of sexual desire	0	1	2	3	4
b. Your ability to have an erection	0	1	2	3	4
c. Your ability to reach an orgasm	0	1	2	3	4

25. Overall, how big a problem has your sexual function or lack of sexual function been for you **during the last 4 weeks?**

- No problem..... 1
- Very small problem..... 2
- Small problem..... 3 (Circle one number)
- Moderate problem..... 4
- Big problem..... 5

### **HORMONAL FUNCTION**

The next section is about your hormonal function. Please consider **ONLY THE LAST 4 WEEKS**.

26. **Over the last 4 weeks**, how often have you experienced hot flashes?

- More than once a day..... 1
- About once a day..... 2
- More than once a week..... 3 (Circle one number)
- About once a week..... 4
- Rarely or never..... 5

27. How often have you had breast tenderness **during the last 4 weeks?**

- More than once a day..... 1
- About once a day..... 2
- More than once a week..... 3 (Circle one number)
- About once a week..... 4
- Rarely or never..... 5

28. **During the last 4 weeks**, how often have you felt depressed?

- More than once a day..... 1
- About once a day..... 2
- More than once a week..... 3 (Circle one number)
- About once a week..... 4
- Rarely or never..... 5

29. **During the last 4 weeks**, how often have you felt a lack of energy?

- More than once a day..... 1
- About once a day..... 2
- More than once a week..... 3 (Circle one number)
- About once a week..... 4
- Rarely or never..... 5

30. How much change in your weight have you experienced **during the last 4 weeks**, if any?

- Gained 10 pounds or more.....1
- Gained less than 10 pounds .....2
- No change in weight.....3 (Circle one number)
- Lost less than 10 pounds .....4
- Lost 10 pounds or more.....5

31. How big a problem **during the last 4 weeks**, if any, has each of the following been for you?  
 (Circle one number on each line)

	No Problem	Very Small Problem	Small Problem	Moderate Problem	Big Problem
a. Hot flashes.....	0	1	2	3	4
b. Breast tenderness/enlargement.....	0	1	2	3	4
c. Loss of Body Hair.....	0	1	2	3	4
d. Feeling depressed.....	0	1	2	3	4
e. Lack of energy.....	0	1	2	3	4
f. Change in body weight.....	0	1	2	3	4

**Overall Satisfaction**

32. Overall, how satisfied are you with the treatment you received for your prostate cancer?

- Extremely dissatisfied..... 1
- Dissatisfied..... 2
- Uncertain..... 3      (Circle one number)
- Satisfied..... 4
- Extremely satisfied..... 5

**THANK YOU!!**

**13.7 Appendix VII**

**TREATMENT FORM – Page 1 of 1**

1. Name \_\_\_\_\_ (last) \_\_\_\_\_ (first)

2. RT Number \_\_\_\_\_

3. MRI scan for planning:  yes  
 no

4. Tumor category:  Prostate Cancer, Low Risk  
 Prostate Cancer, Intermediate Risk  
 Prostate Cancer, High Risk

5. Tumor Details:

Maximum Diameter (cm)	GTV Volume (cc)	PTV Margin (mm)						PTV Volume (cc)
		A	P	R	L	S	I	

6. Treatment Portal Design:

- Static gantry angle (coplanar), specify number of fields \_\_\_\_\_
- Static gantry angle (non-coplanar), specify number of fields \_\_\_\_\_
- Dynamic arc (coplanar), specify number of arcs \_\_\_\_\_
- Dynamic arc (non-coplanar), specify number of arcs \_\_\_\_\_

7. Premedication:

- Flomax dose \_\_\_\_\_ mg, start date \_\_\_\_\_
- Amifostine, dose 1500 mg PR
- Bowel Prep, Stool softener, specify drug \_\_\_\_\_, and Fleet enema
- Anti-anxiety, specify drug \_\_\_\_\_, dose \_\_\_\_\_ mg,
- Deca-dron, specify dose \_\_\_\_\_ mg
- Analgesics, specify drug \_\_\_\_\_, dose \_\_\_\_\_ mg

8. Dose-Fractionation Scheme:

Total Dose (Gy)	Dose per Fx (Gy)	# Fx	Prescription IDL (%)	D max (Gy)
36.25	7.25	5		

9. Dose to Normal Tissues:

STRUCTURE	VOLUME	CONSTRAINT(Gy)	DOSE (Gy)
Spinal Cord	D max	22.5	
	< 10 cc	20	
Cauda Equina	D max	27.5	
	< 10 cc	25	
Sacral Plexus	D max	30	
	< 10 cc	27.5	
Anterior Rectal Wall	D max	38	
Posterior Rectal Wall	D max	20	
Lateral Rectal Wall Cumulative (L & R)	D max	36.25	
	< 3 cc	50	
Rectum superior to prostate	D max	30	
	< 10 cc	25	
Small Intestine	D max	30	
	< 10 cc	25	
Prostatic Urethra	D max	38	
Bladder	D max	38	
	< 10 cc	20	
Penile Bulb	D max	38	
	< 3 cc	30	
Femoral Heads Cumulative (L & R)	< 10 cc	30	
Skin not within fold	D max	25	
Skin within fold (e.g. gluteal fold)	D max	20	

Person completing form : Signature \_\_\_\_\_

Print Name \_\_\_\_\_

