The early results of a Canadian phase I/II study (pHART3) using a five-fraction hypofractionated accelerated radiotherapy treatment (35 Gy in five daily fractions) for low risk organ confined prostate cancer were reported by Tang et al. After 6 months of follow up, there was no grade 3 toxicity; however, longer term follow-up is required to assess efficacy and toxicity. (10) Madsen et al. reported on 40 patients treated with SBRT for low risk prostate cancer. They all received 33.5 Gy in five fractions, which is equivalent to 78 Gy in 2 Gy fractions based on alpha/beta ratio of 1.5. The actuarial 4-year biochemical progression-free survival was 90% with a median follow-up of 41 months. There were only two cases of grade 3 acute urinary toxicity. No late toxicity more than grade 3 was reported. (11) King et al. recently reported the Stanford experience of treating 41 low-risk prostate cancer patients with 5 fractions of 7.25 Gy (36.25 Gy) using image-guided SBRT. After a median follow-up of 33 months, they reported no biochemical failure with early and late toxicity profiles no worse than conventional EBRT. In fact, they reported no patients with grade 4 or higher toxicities, only two patients with grade 3 late urinary toxicity and no grade 3 late rectal toxicity. In a separate report, they used the Expanded Prostate Cancer Index Composite (EPIC)-validated quality of life questionnaire to survey 32 consecutive patients treated with SBRT. The mean EPIC sexual domain summary score, sexual function score, and sexual bother score decreased by 45%, 49%, and 25% respectively after 50 months of follow-up. The radiation dose to the penile bulb was not associated with erectile dysfunction. The investigators concluded that the rates of erectile dysfunction appeared comparable to those reported for other modalities of radiotherapy. (12-14)

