Katz et al. (16) also recently published their results with SBRT for localized prostate cancer. Three hundred and four patients were treated as follows: 50 received 5 fractions of 7 Gy (total dose 35 Gy) and 254 received 5 fractions of 7.25 Gy (total dose 36.25 Gy). Two low risk patients and two high risk patients failed biochemically. However, biopsy revealed both of the low risk patients and one of the high risk patients to be disease free in the prostate gland. In this study, rectal administration of amifostine was given prior to each treatment which likely assisted in keeping toxicity low. In fact, despite higher therapeutic doses based on biological equivalent dose (BED) calculations, the observed rate of acute urinary and rectal toxicity was low, with less than 5% of patients experiencing any acute grade II urinary or rectal toxicity and none experiencing any higher grade toxicity. Late toxicity was also less in the recent study using rectal amifostine when compared to previously published studies. For instance, King et al. reported late grade II urinary toxicity in 24% of patients (33-month follow-up) compared to 2% for the 35 Gy dose level (30-month follow-up) and 5.8% for the 36.25 Gy dose level (11-month follow-up). Regarding late bowel effects, King et al. observed 15% grade II toxicity at 33 month median follow-up. Katz et al. observed a late bowel toxicity rate of 4.2% for grade I toxicity and no higher grade toxicity for the 35 Gy dose level with 30 months of follow-up. They attribute their low bowel toxicity rate to the rectal administration of amifostine prior to SBRT delivery. (12, 16) Amifostine has been reported to significantly reduce the incidence of radiation-induced toxicity in multiple studies and when administered rectally has no related toxicity as opposed to intravenous administration which can cause significant

nausea. In both of these studies, late toxicity rates may increase with more follow-up, but what has been reported thus far is encouraging.

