##### **7.2 Dose-Specification**

- 7.2.1 The total prescription dose for SBRT will be 30 – 40 Gy in 4 – 5 fractions delivered 2 to 3 times per week. The total prescription dose for SBRT as a boost after prior conventionally fractionated external beam pelvic radiotherapy (45 Gy in 25 fractions) will be 19 – 21 Gy in 2 – 3 fractions delivered 2 to 3 times per week. At the discretion of the treating radiation oncologist, an integrated boost of ~ 1 Gy per fraction may be directed at the MR abnormality.

- 7.2.2 Radiation beams will conform to the PTV outline without additional margin and the dose will be prescribed to the isodose line (IDL) that covers at least 95% of the PTV. The 105% IDL should be confined to the PTV.
- 7.2.3 Conformality index (CI) = Prescription IDL volume / PTV volume  
Goal =  $CI \leq 1.2$
- 7.2.4 Gradient index (GI) = 50% Prescription IDL volume / Prescription IDL volume  
Goal =  $GI \leq 3$

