### **7.3 Normal Tissue Dose Constraints**

- 7.3.1 The normal structures that will be contoured using the planning CT/MR fusion are listed below with their respective dose constraints (five fractions) as derived from the available literature:

STRUCTURE	VOLUME	DOSE
Spinal Cord	D max	22.5 Gy
	< 10 cc	20 Gy
Cauda Equina	D max	27.5 Gy
	< 10 cc	25 Gy
Sacral Plexus	D max	30 Gy
	< 10 cc	27.5 Gy
Anterior Rectal Wall	D max	No more than 105% Rx
Posterior Rectal Wall	D max	20 Gy
Lateral Rectal Wall	D max	No more than 100% Rx
	< 3 cc cumulative (both sides)	50 Gy
Rectum superior to prostate	D max	30 Gy
	< 10 cc	25 Gy
Small Intestine	D max	30 Gy
	< 10 cc	25 Gy
Prostatic Urethra	D max	No more than 105% Rx
Bladder	D max	No more than 105% Rx
	< 10 cc	20 Gy
Penile Bulb	D max	No more than 105% Rx
	< 3 cc	30 Gy
Femoral Heads	< 10 cc cumulative (both sides)	30 Gy
Skin not within fold	D max	25 Gy
Skin within fold (e.g. gluteal fold)	D max	20 Gy

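### The treatment form (Appendix VII) prints fixed maximum doses of 38 and 36.25 Gy, which fit a prescription of about 36.25 Gy, while 7.3.1 sets these limits as percentages of a prescription that may be 30–40 Gy

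*Combined protocol and SAP*

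**What the plan says.** Section 7.2.1 gives a range for monotherapy: "The total prescription dose for SBRT will be 30 – 40 Gy in 4 – 5 fractions delivered 2 to 3 times per week". Section 7.3.1 then lists normal-tissue limits. Most are fixed doses, but five maxima depend on the prescription. Four of them (anterior rectal wall, prostatic urethra, bladder, penile bulb) read "No more than 105% Rx", and the lateral rectal wall reads "No more than 100% Rx".

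Appendix VII, the treatment form, handles the same limits differently. Item 8, "Dose-Fractionation Scheme", comes already filled in with 36.25 Gy total, 7.25 Gy per fraction and 5 fractions. Item 9, "Dose to Normal Tissues", has a constraint column in Gy next to an empty column for the achieved dose. There the four 105% limits appear as 38 Gy, and the maximum in the row "Lateral Rectal Wall Cumulative (L & R" appears as 36.25 Gy. The form does not mention a percentage and has no space for a recalculated limit.

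**The concern.** The form sets each patient's achieved dose directly beside the limit it should respect. If the printed limit belongs to one prescription and the patient received another, the comparison misleads. Below 36.25 Gy it errs in the lenient direction, for the rectum, bladder and urethra among others, and late toxicity is the secondary endpoint (2.3.2). Section 11.2 names strict compliance with the 7.3 constraints as one of the ways risk is kept down, so the reference value used in that check should be right for every prescription the protocol permits.

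Other doses are a realistic prospect. The Introduction supports the regimen with five-fraction series inside the permitted range. Of one it says "They all received 33.5 Gy in five fractions", and of another "50 received 5 fractions of 7 Gy (total dose 35 Gy) and 254 received 5 fractions of 7.25 Gy (total dose 36.25 Gy".

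**Working it through.** **Inputs.** Prescription (Rx) range 30–40 Gy from 7.2.1. Limits of 1.05 × Rx (four structures) and 1.00 × Rx (lateral rectal wall) from 7.3.1. Printed values of 38 and 36.25 Gy, and the pre-printed scheme of 7.25 Gy × 5, from Appendix VII items 8 and 9. Cited five-fraction doses of 33.5, 35 and 36.25 Gy from the Introduction.

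**Reproducing the form.** Rx = 5 × 7.25 = 36.25 Gy. Then 1.05 × 36.25 = 38.06, printed as 38, and 1.00 × 36.25 = 36.25. The form agrees with itself.

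**Where the printed values remain right.**

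- A 105% limit rounds to 38 Gy when it lies between 37.5 and 38.5 Gy, so Rx must lie between 37.5/1.05 = 35.71 Gy and 38.5/1.05 = 36.67 Gy.
- The lateral wall entry is given to two decimals, so it is right only at 36.25 Gy. At 36 Gy it is already 36.25 − 36 = 0.25 Gy too high.

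**Printed value minus the 7.3.1 limit, five-fraction monotherapy.**

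| Rx (Gy) | 105% limit (Gy) | 38 minus limit | 100% limit (Gy) | 36.25 minus limit |
|---|---|---|---|---|
| 30 | 31.5 | +6.5 | 30 | +6.25 |
| 33.5 | 35.175 | +2.83 | 33.5 | +2.75 |
| 35 | 36.75 | +1.25 | 35 | +1.25 |
| 36.25 | 38.06 | −0.06 (rounding) | 36.25 | 0 |
| 40 | 42 | −4 | 40 | −3.75 |

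A plus sign means the form is more lenient than the protocol, a minus sign that it is stricter. As a share of prescription, 38 Gy is 38/30 = 126.7% at the bottom of the range and 38/40 = 95.0% at the top. For 36.25 Gy the shares are 120.8% and 90.6%.

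**How many rows.** Item 9 prints 22 limits. Five are the converted percentages, and the other 17 have the same values as in 7.3.1.

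**Example.** A patient is prescribed 35 Gy in 5 fractions, and the bladder maximum, at a point inside the planning target volume (PTV) margin, is 37.5 Gy. The protocol limit is 1.05 × 35 = 36.75 Gy. Since 36.75 < 37.5 < 38, the plan breaches 7.3.1 but passes against the printed value.

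**The case against.** The best defence is that the form is a template for the site's usual scheme. Its conversions are correct. Anyone treating at another dose has to overwrite item 8, and would then see that the limits in item 9 belong to the dose just replaced. The extracted text cannot show whether those cells are editable defaults. Much of this stands: there is no arithmetic error, only a conflict between the form and 7.2.1 with 7.3.1. But nothing tells staff to recalculate item 9, no other treatment form is supplied, and item 8 leaves other plan-specific cells (prescription isodose, maximum dose) blank. As written, the limits are wrong for permitted prescriptions.

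Three further points limit the weight.

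- Section 7.2.2 separately says that the 105% isodose should stay within the PTV. At 35 Gy, a bladder point outside the PTV receiving 37.5 Gy (107% of prescription) would depart from 7.2.2 whatever the form prints. The example therefore matters where bladder lies inside the PTV margin.
- The largest differences need 30 or 40 Gy in five fractions. Both are permitted, but no cited five-fraction series used either. At the cited in-range doses the form is lenient by at most 2.83 Gy.
- Above about 36.7 Gy the printed values are too strict. That could cause a false alarm but not a missed breach.

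A reader might infer that the form authorises doses above the protocol limits, or that the trial's results are affected. The documents do not support either. Section 11.2 points to 7.3 and not to the form; the achieved dose, which 2.2.3 lists as study data, is still written down; and 11.5 plans no analysis of constraint compliance. A reader might also carry 38 Gy across to the 19–21 Gy boost and call it 181–200% of prescription. The table in 7.3.1 is labelled for five fractions, so the documents do not establish that comparison.

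**Conclusion.** The inconsistency is real and minor. Five of the 22 limits in Appendix VII are wrong as written for most of the permitted monotherapy range: the four 38 Gy entries outside about 35.7–36.7 Gy, and the 36.25 Gy entry at any dose other than 36.25 Gy. At 35 Gy, a dose the Introduction cites, a plan could exceed the protocol limit by up to 1.25 Gy and still pass against the form. Because 7.3.1 governs and the achieved dose is recorded, compliance can be recalculated for every patient; no data are lost and no endpoint changes.

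This rests on two assumptions: that any dose from 30 to 40 Gy may be given in five fractions, since 7.2.1 does not tie doses to fraction numbers, and that the form is used as printed for all five-fraction monotherapy patients, since no text restricts it to 36.25 Gy.

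**What to change.** In Appendix VII item 8, leave total dose, dose per fraction and number of fractions blank. In item 9, replace each of the four 38 Gy entries with `105% × prescription = ____ Gy`, and the lateral rectal wall maximum of 36.25 Gy with `100% × prescription = ____ Gy`. The other 17 entries need no change for this point.

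The cost is three blanked fields and five reworded entries, with no extra patients, visits or procedures. For forms already completed at another dose, the five limits can be recalculated from the recorded prescription and compared with the recorded doses.
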